6.1.5 Hypertension toxicity

Therapeutic BP monitoring by a health care provider will occur every 2 weeks during the first 2 cycles then at least every cycle for the duration of treatment in the dose escalation phase, and on D1 and D8 of cycle 1 then at least every cycle in the expansion phase. All patients will be required to monitor their BP at least once a day (preferably BID) throughout the treatment and record the readings in the study diary ([Appendix E](#)). Table 3 will be used for the grading of pazopanib-associated hypertension, for immediate and long-term management, and for the determination of pazopanib dose modification. Suggested antihypertensive medications are listed in Table 4.

Table 3: Recommended Hypertension Monitoring and Management (BP in mmHg)

Grade (CTCAE v4)	Antihypertensive Therapy	Blood Pressure Monitoring	Pazopanib Dose Modification
Persistent Grade 1 Pre-hypertension Systolic 120-139 Diastolic 80-90		Standard	No Change
Persistent Grade 2-Moderate Systolic 140-159 Diastolic 90-99	
Step 1) Initiate BP treatment and if needed, after 24-48 hr of treatment, increase dose in stepwise fashion every 24-48 hours until BP is controlled or at maximum dose of medication
 
Step 2) If BP still not controlled, add another anti-hypertensive medication, a LA DHP CCB, ACE1, ARB, or ABB; increase dose of this drug as described in step 1
 
Step 3) If BP still not controlled, add 3rd drug from the list of antihypertensives in step 2; increase dose of this drug as described in step 1
 
Step 4) If BP still not controlled, consider either 1 dose reduction of pazopanib or stopping pazopanib
	BP should be monitored as recommended by the treating physician	No change except as described in step 4

Grade (CTCAE v4)	Antihypertensive Therapy	Blood Pressure Monitoring	Pazopanib Dose Modification
	
NOTE: Stopping or reducing the dose of pazopanib is expected to cause a decrease in BP. The treating physician should monitor the subject for hypotension and adjust the number and dose of antihypertensive medication(s) accordingly
		

Persistent Grade 3 Severe Systolic ≥ 160 Diastolic ≥ 100
	
HOLD pazopanib until systolic BP ≤ 159 and diastolic BP ≤ 99.
 
BP management is identical to that for Grade 2 (see steps 1-4 above) with 2 major exceptions:
 
1) If systolic BP >180 or diastolic BP >110 and the subject is symptomatic: optimal management with intensive IV support in ICU; STOP pazopanib and notify hospital staff that stopping pazopanib may result in a decrease in BP and
 
2) If systolic BP >180 or diastolic BP >110 and the subject is asymptomatic, 2 new antihypertensives must be given together in step 1 (and dose escalated appropriately as in step 1).
 
NOTE: Stopping or reducing the dose of pazopanib is expected to cause a decrease in BP. The treating physician should monitor the subject for hypotension and adjust the number and dose of antihypertensive medication(s) accordingly
	
BP should be monitored as recommended by the treating physician unless the subject is symptomatic with systolic BP >180 or diastolic BP >110 in which case, monitoring should be intensive.
	
HOLD pazopanib until systolic BP ≤ 159 and diastolic BP ≤ 99. After this, pazopanib may be re-administered. If BP is still grade 2, manage as described above for grade 2 hypertension.
 
In most circumstances, if BP cannot be controlled after an optimal trial of antihypertensive medications, consider either 1 dose reduction of pazopanib when systolic BP ≤ 159 and diastolic BP ≤ 99 or stopping pazopanib.
 
HOWEVER, If the subject requires hospitalization for management of symptomatic systolic BP >180 or diastolic BP >110, permanently discontinue pazopanib or if BP is controlled to systolic BP ≤ 159 and diastolic BP ≤ 99, consider re-starting pazopanib at 1 lower dose level after consultation with the study Principal Investigator

Grade 4 Life-threatening consequences of hypertension
	
Optimal management with intensive IV support in ICU; STOP pazopanib and notify hospital staff that stopping pazopanib may result in a decrease in BP
	
Intensive
	
Permanently discontinue pazopanib or if systolic BP ≤ 159 and diastolic BP ≤ 99, consider re-starting pazopanib at 1 lower dose level after consultation with the study Principal Investigator


Abbreviations: Dihydropyridine calcium-channel blockers (DHP-CCB), selective beta blockers (BB), Angiotensin Converting Enzyme Inhibitors (ACEI), Angiotensin II Receptor Blockers (ARB), alpha beta blocker (ABB)
 
 *See table below for suggested antihypertensive medications by class 			

Grade (CTCAE v4)	Antihypertensive Therapy	Blood Pressure Monitoring	Pazopanib Dose Modification
	
 • If subjects require a delay of >2 weeks for management of hypertension, discontinue protocol therapy • If subjects require >2 dose reductions, discontinue protocol therapy • Subjects may have up to 2 drugs for management of hypertension prior to any dose reduction in pazopanib • 24-48 hours should elapse between modifications of antihypertensive therapy • Hypertension should be graded using CTCAE v4 		

Notes:

- While patients are receiving treatment with pazopanib, the early initiation of antihypertensive treatment for grade 1 or 2 hypertension to minimize more severe or persistent hypertension is not considered a grade 3 adverse event.
- Decisions to hold or decrease the pazopanib dose during treatment must be based on BP readings taken in the clinic by a medical professional.
- Based on prior clinical experience with pazopanib, the use of calcium channel blockers (dihydropyridine category) and ACE inhibitors as first-line and second-line therapy is recommended.

Table 4: Oral Antihypertensive Medications: Agents in bold characters are suggested as optimal choices to avoid or minimize potential drug-interactions with pazopanib through CYP450.

Agent class	Agent	Initial dose	Intermediate dose	Maximum dose	Hepatic metabolism
Dihydro-pyridine Calcium-Channel Blockers (DHP CCB)	nifedipine XL	30 mg daily	60 mg daily	90 mg daily	CYP 3A4 substrate
	amlodipine	2.5 mg daily	5 mg daily	10 mg daily	CYP 3A4 substrate
	felodipine	2.5 mg daily	5 mg daily	10 mg daily	CYP 3A4 substrate and inhibitor
Selective β Blockers (BB)	metoprolol	25 mg twice daily	50 mg twice daily	100 mg twice daily	CYP 2D6 substrate
	atenolol	25 mg daily	50 mg daily	100 mg daily	No
	acebutolol	100 mg twice daily	200-300 mg twice daily	400 mg twice daily	Yes (CYP450 unknown)
	bisoprolol	2.5 mg daily	5-10 mg daily	20 mg daily	Yes (CYP450 unknown)
Angiotensin Converting Enzyme Inhibitors (ACEIs)	captopril	12.5 mg 3x daily	25 mg 3x daily	50 mg 3x daily	CYP 2D6 substrate
	enalapril	5 mg daily	10-20 mg daily	40 mg daily	CYP 3A4 substrate
	ramipril	2.5 mg daily	5 mg daily	10 mg daily	Yes (CYP450 unknown)
	lisinopril	5 mg daily	10-20 mg daily	40 mg daily	No
	fosinopril	10 mg daily	20 mg daily	40 mg daily	Yes (CYP450 unknown)
	Rarely used: perindopril	4 mg daily	none	8 mg daily	Yes, but not CYP450
	Rarely used: quinapril	10 mg daily	20 mg daily	40 mg daily	No
Angiotensin II	losartan	25 mg daily	50 mg daily	100 mg daily	CYP 3A4 substrate

Agent class	Agent	Initial dose	Intermediate dose	Maximum dose	Hepatic metabolism
Receptor Blockers (ARBs)	candesartan	4 mg daily	8-16 mg daily	32 mg daily	CYP 2C9 substrate
	irbesartan	75 mg daily	150 mg daily	300 mg daily	CYP 2C9 substrate
	telmisartan	40 mg daily	none	80 mg daily	Yes, but not CYP450
	valsartan	80 mg daily	none	160 mg daily	Yes, but not CYP450
α and β Blocker	labetolol	100 mg twice daily	200 mg twice daily	400 mg twice daily	CYP 2D6 substrate and inhibitor

6.1.6 Proteinuria toxicity

Evaluation of urine protein/creatinine ratio (UPC) should occur as follows:

- *Dose escalation phase*: at baseline, on C1D15, then at the start of each cycle
- *Expansion phase*: at baseline, on C1D8, then at the start of each cycle.

If, at any time, a subject has a urine protein/creatinine ratio greater than 1, a 24 hour urine collection must be performed. If a subject develops the nephrotic syndrome, treatment must be discontinued.

Although subjects with ≥1+ proteinuria at entry are ineligible, increases in proteinuria may occur during treatment and should be managed as Table 5:

Table 5: Pazopanib Dose Modifications for Proteinuria Toxicity

UPC > 1 and < 3	Obtain 24-hr urine protein and if <3 g, continue at current dose and monitor as clinically indicated
UPC ≥ 3 or 24-h urine protein ≥ 3 g	Step 1. Interrupt pazopanib. Step 2. Weekly UPC or 24-hr urine protein monitoring until UPC is <3 or 24-hr urine protein is <3 grams. Then restart pazopanib dose-reduced by 200 mg. Step 3. If UPC >3 or 24-h urine protein ≥3g recurs, repeat steps 1 and 2 Step 4. If UPC ≥3 or 24-hr urine protein ≥3 recurs and the pazopanib dose can no longer be reduced, discontinue pazopanib and remove subject from study.
Nephrotic syndrome	Permanently discontinue pazopanib and remove subject from study

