3.2.9 Patients who received major surgery within the past 4 weeks

3.2.10 Subjects with any condition that may impair the ability to swallow or absorb oral medications/investigational product including:

- any lesion, whether induced by tumor, radiation or other conditions, which makes it difficult to swallow capsules or pills
- prior surgical procedures affecting absorption including, but not limited to major resection of stomach or small bowel
- active peptic ulcer disease
- malabsorption syndrome

3.2.11 Subjects with any condition that may increase the risk of gastrointestinal bleeding or gastrointestinal perforation, including

- active peptic ulcer disease
- known intraluminal metastatic lesions
- inflammatory bowel disease (e.g., ulcerative colitis, Crohn's disease) or other gastrointestinal conditions which increase the risk of perforation
- history of abdominal fistula, gastrointestinal perforation or intra-abdominal abscess within 28 days prior to beginning study treatment

3.2.12 History of hemoptysis in excess of 2.5 mL (1/2 teaspoon) within 8 weeks prior to first dose of study drug.

3.2.13 Urine protein/creatinine ratio should be screened by urine analysis. If protein is 1+ or higher, 24-hour urine protein should be obtained and the level should be < 1 g for patient enrollment. Patients with < 1+ proteinuria are eligible following initial determination by urinalysis within 1 week prior to enrollment and do not need the urinalysis repeated.

3.2.14 Patients with clinically significant intercurrent illnesses, including but not limited to, life threatening infection, psychiatric illness/social situations that would limit compliance with study requirements will not be eligible to participate.

3.2.15 Pregnant women are excluded from this study because the effects of the study drugs on the developing fetus are unknown. Because there is an unknown but potential risk for adverse events in nursing infants secondary to treatment of the mother with the study drugs, breastfeeding should be discontinued prior to the first dose of study drug and women should refrain from nursing throughout the treatment period and for 14 days following the last dose of study drug.

3.2.16 HIV-positive patients on combination antiretroviral therapy are ineligible because of the potential for PK interactions.

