6 DOSING DELAYS/DOSE MODIFICATIONS

Toxicities (hematologic and non-hematologic; except any grade lymphopenia, anemia, or alopecia) should have resolved to \leq Grade 2 prior to starting the next cycle or receiving the next dose of pazopanib or ARQ 197 within a cycle. Study drugs should be held for hypokalemia or hyperkalemia \geq grade 2; hypocalcemia or hypercalcemia \geq grade 3; hypophosphatemia \geq grade 3; hypomagnesemia or hypermagnesemia \geq grade 3. These laboratory values should be corrected as soon as possible in a manner consistent with good medical judgment. Study drugs may be re-administered when hypokalemia or hyperkalemia is grade 1 or within institutional limits; hypocalcemia or hypercalcemia is \leq grade 2; hypophosphatemia is \leq grade 2; and hypomagnesemia or hypermagnesemia is \leq grade 2. Even though study drug administration is allowed at these lower grades, every effort should be made to correct the abnormal lab values to normal if possible. If the potassium level is grade 2 or greater and/or if the calcium, magnesium, and/or phosphate are grade 3 or higher, an EKG must be performed and appropriate action taken based on the results.

Treatment may be delayed for a maximum of 2 weeks for toxicities. In case toxicities do not resolve as stated, the patient will not receive further therapy on this protocol and will be followed for resolution of toxicities. Start of next cycle may be delayed for up to 1 week to accommodate scheduling conflicts. Dose modifications are intended for within-cycle and start-of-next-cycle changes. If administration of study drug is interrupted for any reason, it will not be made up, and

counting of the cycle days continues (i.e., if a patient stops pazopanib and ARQ 197 on day 15 and resumes 2 days later, they will be considered day 17).

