10.1 Dose Escalation Phase

	Pre-Study	C1 W1 (D1-7)	C1 W2 (D8-14)	C1 W3 (D15-21)	C1 W4 (D22-28)	C2 W1 (D1-7)	C2 W2 (D8-14)	C2 W3 (D15-21)	C2 W4 (D22-28)	C3 W1 on	Off Treatment
Pazopanib^a		X	X	X	X	X	X	X	X	X	
ARQ 197^a		X	X	X	X	X	X	X	X	X	
Informed consent	X										
Demographics	X										
Medical history	X										
Concurrent meds	X	X-----X									
Physical exam ^b	X			X		X				X	X
Vital signs ^c	X			X		X		X		X	X
Height	X										
Weight	X					X				X	X
Performance status	X					X				X	X
CBC w/diff, plts ^d	X		X	X	X	X		X		X	X
Serum chemistry ^d	X		X	X	X	X		X		X	X
Coagulation	X										
Urine protein/creatinine ratio or 24-hour urine protein ^e	X			X		X				X	X
EKG ^f	X			X							
Echocardiogram/MUGA	X										
Adverse event evaluation		X-----X									X
Tumor measurements	X	Tumor measurements are repeated every 2 cycles. Documentation (radiologic) must be provided for patients removed from study for progressive disease.									X
B-HCG ^g	X										
Tumor biopsies ^h	X		X								
PD blood sampling ⁱ	X	X		X		X					
PG blood sampling ^j	X										
PK blood sampling ^k	X	X		X							

- a: Pazopanib once daily (empty stomach) and ARQ 197 twice daily (with meals) at the assigned dose.
- b: Physical examination at Clinical Center should be performed on day 1 and day 15, and then at the start of each cycle (up to 3 days before start of new cycle). For patients who have been on study for 6 or more cycles and are tolerating treatment well, physical exams may be performed once every 2 cycles (every 2 months).
- c: BP monitoring by a health care provider should be performed every 2 weeks during the first 2 cycles and then at the beginning of subsequent cycles. For patients who have been on study for 6 or more cycles and are tolerating treatment well, BP monitoring may be performed once every 2 cycles (every 2 months). Mid-cycle BP check can be performed by any health care professional. Patients should measure and record their blood pressure at home at least once per day for the duration of the study.
- d: Serum chemistry (albumin, alkaline phosphatase, total bilirubin, BUN, calcium, creatinine, glucose, phosphorus, magnesium, potassium, total protein, SGOT [AST], SGPT [ALT], sodium) and CBC w/diff, platelets should be performed within 72 hours of enrollment (pre-study) and weekly during cycle 1 (D8, D15 and D22 ± 1 day for scheduling conflicts), every 2 weeks during cycle 2 (± 1 day for scheduling

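### Table 5's restart rule for proteinuria does not mirror its hold rule, so a patient held on one urine measure can be cleared on the other

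*Combined protocol and SAP*

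**What the plan says.** Section 6.1.6 and its Table 5 set four rules that bear on this point.

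- **Collection rule.** The text above the table covers any patient who at any time has "a urine protein/creatinine ratio greater than 1, a 24 hour urine collection must be performed".
- **Continue row (UPC above 1 and below 3).** "Obtain 24-hr urine protein and if <3 g, continue at current dose and monitor as clinically indicated".
- **Hold row.** Pazopanib is interrupted (Step 1) at a UPC of 3 or more, or a 24-hour protein of 3 g or more. Either is enough.
- **Restart (Step 2).** "Weekly UPC or 24-hr urine protein monitoring until UPC is <3 or 24-hr urine protein is <3 grams", after which pazopanib resumes 200 mg lower.

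Step 3 covers recurrence: "If UPC >3 or 24-h urine protein ≥3g recurs, repeat steps 1 and 2". The hold row and Step 4 use 3 or more for UPC, so Step 3 differs by one symbol.

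Section 6 adds two general rules. Toxicities should be at Grade 2 or lower "prior to starting the next cycle or receiving the next dose of pazopanib or ARQ 197 within a cycle", and "Treatment may be delayed for a maximum of 2 weeks for toxicities".

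**The concern.** A rule that starts a hold when either of two measures is high should end it only when neither is high. Step 2 joins its two recovery conditions with 'or'. A patient whose UPC lies between 1 and 3, and who is held because the 24-hour collection came back at 3 g or more, has a UPC below 3 by construction. For that patient one limb of the restart condition was never breached.

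The plan itself foresees such discordance, since the continue row exists to catch it. Elsewhere, too, the 24-hour value settles an abnormal screening result: under exclusion criterion 3.2.13, if urinalysis protein is 1+ or higher, "24-hour urine protein should be obtained and the level should be < 1 g for patient enrollment". The neighbouring hold for Grade 3 hypertension (Table 3) ends only when systolic and diastolic pressure have both come down.

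At stake is whether pazopanib can be restarted, at a lower dose, while the measure that stopped it is still at or above its limit.

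**Working it through.** The plan states no figure to reproduce. The check is one of logic, followed by a rough size for the discordant range.

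**1. Hold against restart.** Write U for UPC and P for 24-hour protein in grams.

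- Hold (Table 5, row 2): U ≥ 3 or P ≥ 3.
- Literal restart (Step 2): U < 3 or P < 3.
- True complement of the hold: U < 3 and P < 3.

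| UPC | 24-h protein | Hold? | Literal restart met? | 24-h collection required? |
|---|---|---|---|---|
| ≤1 | <3 g | no | yes | no |
| ≤1 | ≥3 g | **yes** | **yes** | no |
| >1 to <3 | <3 g | no | yes | yes |
| >1 to <3 | ≥3 g | **yes** | **yes** | yes |
| ≥3 | <3 g | **yes** | **yes** | yes |
| ≥3 | ≥3 g | yes | no | yes |

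Four of the six pairs call for a hold, and three of those four also meet the literal restart condition. These are result pairs, not patients. With 'and' in place of 'or', the overlap is 0. Example: UPC 2.5 with 24-hour protein 3.5 g is in the hold row and also meets Step 2.

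**2. What staff would see.** In two of the three overlapping pairs UPC is above 1, so the 24-hour collection is compulsory and the value is known. The fault there is two opposite instructions for the same results. In the third (UPC 1 or less, 24-hour protein 3 g or more) no collection is required, and UPC alone can clear the restart.

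**3. Width of the discordant range.** If the spot ratio equals the 24-hour ratio, P = U × C, where C is 24-hour creatinine excretion in grams. P reaches 3 g at U = 3/C. The documents do not give C; 0.8 to 2.0 g/day is an assumption.

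| C (g/day) | UPC at which P = 3 g | Discordant UPC range |
|---|---|---|
| 0.8 | 3/0.8 = 3.75 | 3.0 to 3.75 (held on UPC, P below 3 g) |
| 1.0 | 3/1.0 = 3.0 | none |
| 1.2 | 3/1.2 = 2.5 | 2.5 to 3 (held on P, UPC below 3) |
| 1.5 | 3/1.5 = 2.0 | 2.0 to 3 (held on P) |
| 2.0 | 3/2.0 = 1.5 | 1.5 to 3 (held on P) |

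For the unchecked pair, U ≤ 1 with P ≥ 3 needs C of at least 3/1 = 3.0 g/day, outside the assumed range. It would arise mainly through spot-sample variation.

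**4. Step 3.** UPC above 3 and UPC of 3 or more differ only at exactly 3. At UPC 3.0 with 24-hour protein 2.5 g the hold row applies but Step 3 does not.

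**The case against.** The best defence is that Step 2 pairs each test with its own threshold: follow UPC until UPC is below 3, or follow 24-hour protein until that is below 3 g. This is a natural reading. The protocol often treats the tests as alternatives, as in eligibility criterion 3.1.9 and the calendar row "Urine protein/creatinine ratio or 24-hour urine protein". But it closes the gap only if the test followed is the one that set the hold, and Step 2 does not say so.

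A reader might infer that the drug can be restarted on the day it is stopped. The documents do not support that. Step 1 interrupts, Step 2 monitors weekly, and only then does dosing resume, which implies a later measurement.

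A reader might also infer that heavy proteinuria would routinely go unseen. That is not supported either. Above a UPC of 1 the collection is compulsory, and a result of 3 g or more carries an explicit instruction to interrupt. That objection stands, and it reduces the usual case to a conflict between instructions.

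The Section 6 requirement of Grade 2 or lower may block the restart. The documents give no proteinuria grade cut-offs, so this cannot be settled from them. Finally, nephrotic syndrome stops treatment whatever Step 2 says, and any restart is at a reduced dose.

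**Conclusion.** The point holds as a minor patient-safety inconsistency, confined to patients whose two urine measures disagree about the threshold. The logical mismatch rests on the text alone. The width of the discordant range rests on the assumed creatinine excretion and on the spot ratio equalling the 24-hour ratio. How often it would occur is unknown.

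The realistic consequence is a restart and an interrupt instruction for the same results when UPC is above 1. The less common one is a restart at UPC 1 or less without repeating the test that set the hold.

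A reader might go further and infer harm to the dose-finding result. Nothing in the documents shows an effect on a DLT call, the MTD or any analysis. Nor do they say that a value still high after restart counts as a recurrence under Step 3, so a second dose reduction on that ground is conjecture. The correction is worth making because a stated dosing rule should not give opposite answers and the change is small.

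**What to change.** Reword Step 2 along these lines: *Monitor weekly with the test that triggered the hold (both, if both were ≥3) until it is below its threshold (UPC <3; 24-hour urine protein <3 g) and no concurrent UPC or required 24-hour result is at or above threshold; then resume pazopanib at a dose 200 mg lower.* In Step 3, change >3 to ≥3 for UPC, as a clerical match to the hold row and Step 4.

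Under this wording no restart can coincide with a result in hand that belongs to the hold row. A 24-hour collection before every restart would go further than needed: a patient held on UPC alone whose UPC has fallen to 1 or less does not need one.

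The cost is an occasional extra weekly 24-hour collection, mainly in patients held on that test whose UPC is 1 or less, since above 1 it is already required. Holds would be slightly longer in discordant patients. At an assumed 1.5 g/day creatinine, a patient held on 24-hour protein would wait until UPC is below about 2.0, not 3. At 0.8 g/day, a patient held on UPC would wait for UPC itself to fall below 3. Some could reach the two-week delay limit, which allows only two weekly checks (days 7 and 14).

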6.1.7 Cardiac Toxicity

1. Discontinue pazopanib in patients who develop symptomatic heart failure.
2. Modify the pazopanib dose using the table presented in [Appendix F](#) in patients who develop compromised symptomatic LVEF. The NCI developed the table in [Appendix F](#) using the NSABP-B31 and NCCTG9831 monitoring guidelines for adjuvant trastuzumab in patients with breast cancer. These studies enrolled populations considered most likely to be cured; thus, the investigators used the most stringent and conservative monitoring.
3. Discontinue ARQ 197 in patients who develop symptomatic bradycardia.

4. Patients with asymptomatic bradycardia will not have drug held or dose modified. Bradycardic patients with a heart rate ≤ 50 beats per minute should have an EKG done on day 1 of every cycle, or as clinically indicated.
5. QTc Prolongation, see Table 6.

Table 6: Management of QTc Prolongation

If EKG reveals an increase in the QTc to ≥ 500 msec or an increase in the QTc by at least 60 msec from baseline	Repeat EKG before re-administration of pazopanib and/or ARQ 197
If repeat EKG shows QTc interval is ≥ 500 msec	Remove subject from study
If on repeat EKG, QTc remains at least 60 msec longer than baseline but is less than 500 msec	Consider removing subject from study

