6.1.8 Management of Subjects with Elevations in AST, ALT and/or Bilirubin

Table 7: Management of Liver Function Test Abnormality

AST, ALT and/or Bilirubin	
Isolated AST/ALT elevations between 3X ULN and 8X ULN	Continue pazopanib, but monitor weekly until AST/ALT returns to ≤ 2.5 or baseline
AST/ALT > 8 X ULN	Hold pazopanib until AST/ALT returns to ≤ 2.5 X ULN or baseline. If the potential benefit of reinitiating pazopanib treatment is considered to outweigh the risk for hepatotoxicity, then consider reintroducing pazopanib at a reduced dose of 400 mg once daily and measure serum liver tests weekly for 8 weeks only after discussion with the PI and CTEP. If AST/ALT elevations > 3 X ULN recur, then pazopanib should be permanently discontinued.
AST/ALT > 3 X ULN and concurrent bilirubin elevations > 2 X ULN	Permanently discontinue pazopanib.
Mild indirect hyperbilirubinemia, known or suspected Gilbert's syndrome, and elevation in ALT > 3 X ULN	Continue pazopanib, but monitor weekly until ALT returns to grade 1 (NCI CTCAE) or baseline.

6.1.9 Reversible Posterior Leukoencephalopathy Syndrome (RPLS) or similar leukoencephalopathy syndrome

RPLS or clinical syndromes related to vasogenic edema of the white matter have been rarely reported in association with pazopanib therapy ($< 3\%$). Clinical presentations are variable and may include altered mental status, seizure, and cortical visual deficit.

Hypertension is a common risk factor in patients who develop RPLS. MRI scans are key to diagnosis and typically demonstrate vasogenic edema (hyperintensity in T2 and FLAIR images and hypointensity in T1 images) predominantly in the white matter of the posterior parietal and occipital lobes; less frequently, the anterior distributions and the

gray matter may also be involved. RPLS should be in the differential diagnosis in patients presenting with unexplained mental status changes, visual disturbance, seizure or other CNS findings. RPLS is potentially reversible, but timely correction of the underlying causes, including control of blood pressure and interruption of the offending drug, is important in order to prevent progression to irreversible tissue damage. Pazopanib should be held in patients with symptoms/signs suggestive of RPLS, pending work-up and management, including control of blood pressure. Pazopanib should be discontinued upon diagnosis of RPLS.

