APPENDIX F: LVEF DOSE MODIFICATION TABLE

Asymptomatic Decrease in LVEF

The decision to continue or hold STUDY DRUG is based on the LVEF as it relates to the institutions’s lower limit of normal (LLN) **and** change in ejection fraction from screening (LVEF as measured at registration) according to the following table:

Relationship of LVEF to institution’s LLN	LVEF Decrease < 10%	LVEF Decrease 10-15%	LVEF Decrease ≥ 16%
Normal	Continue	Continue	Continue and repeat MUGA/ECHO within 1-2 cycles
1-5% below LLN	Continue and repeat MUGA/ECHO within 1-2 cycles	Continue and repeat MUGA/ECHO within 1-2 cycles	HOLD and repeat MUGA/ECHO within 1-2 cycles
≥ 6% below LLN	Continue and repeat MUGA/ECHO within 1-2 cycles	HOLD and repeat MUGA/ECHO within 1-2 cycles	HOLD and repeat MUGA/ECHO within 1-2 cycles

Discontinue STUDY DRUG if:

- Two consecutive HOLD categories occur.
- Three intermittent HOLD categories occur (at the discretion of the investigator, STUDY DRUG may also be permanently discontinued prior to the occurrence of 3 intermittent HOLD categories).

If LVEF is maintained at a “Continue and repeat MUGA/ECHO” or improves from a HOLD to a “Continue and repeat MUGA/ECHO” category, additional MUGA scans/echocardiograms prior to the next scheduled MUGA/ECHO will be at the discretion of the investigator.

Symptomatic Cardiac Events

CTEP Protocol #8880
Clinical Center Protocol #: 12-C-0009

Discontinue STUDY DRUG if:

- A patient has symptoms of congestive heart failure (CHF) and a diagnosis of CHF is confirmed.
- A patient has a myocardial infarction.

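### Section 6.1.7 item 2 applies the Appendix F LVEF table to symptomatic patients, but that table is headed for asymptomatic decreases

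*Combined protocol and SAP*

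**What the plan says.** Section 6.1.7 (Cardiac Toxicity) is a numbered list. Item 1 reads "Discontinue pazopanib in patients who develop symptomatic heart failure". Item 2 begins "Modify the pazopanib dose using the table presented in" Appendix F and gives the population as those "in patients who develop compromised symptomatic LVEF". Items 3 and 4 concern bradycardia: ARQ 197 is stopped if it is symptomatic, and neither holding nor dose change applies if it is not.

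Appendix F has two parts.

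- The first is headed "Asymptomatic Decrease in LVEF". It holds the appendix's only table, which crosses LVEF relative to the institution's lower limit of normal (LLN) with the size of the fall since screening. A typical entry is "Continue and repeat MUGA/ECHO within 1-2 cycles". Discontinuation rules follow the table; one applies when "Two consecutive HOLD categories occur".
- The second covers symptomatic cardiac events. It has no table. It discontinues study drug for myocardial infarction, or when "A patient has symptoms of congestive heart failure (CHF) and a diagnosis of CHF is confirmed".

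**The concern.** The cross-reference and its target describe opposite populations. This is an operative dosing rule, not background text, so a site is entitled to follow it as worded. Doing so would send a patient with symptoms and a reduced LVEF to a grid meant for patients without symptoms, where dosing may continue pending a repeat scan. The patients whom the grid does cover would find no instruction for them in the section that governs cardiac dose changes. What is at stake is the clarity of a safety rule. No analysis depends on it.

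**Working it through.** The plan states no figure here to reproduce, so the check sets the texts side by side.

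| Place | Population | Action |
|---|---|---|
| 6.1.7 item 1 | Symptomatic heart failure | Discontinue pazopanib |
| 6.1.7 item 2 | Compromised LVEF, *symptomatic* | Use the Appendix F table |
| Appendix F, part with the table | LVEF decrease, *asymptomatic* | Continue, continue and rescan, or hold and rescan |
| Appendix F, symptomatic list | Confirmed symptomatic CHF, or myocardial infarction | Discontinue study drug |

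**Could item 2 mean another table?** No. Appendix F has one table, directly under the asymptomatic heading. The appendix's overall title is neutral about symptoms, but it does not displace that heading.

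**What kind of rule is the table?** It has 3 × 3 = 9 cells.

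- LVEF normal: 2 continue, 1 continue and rescan.
- 1–5% below LLN: 2 continue and rescan, 1 hold.
- At least 6% below LLN: 1 continue and rescan, 2 hold.

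That makes 2 + (1 + 2 + 1) = 6 cells that keep dosing and 1 + 2 = 3 that hold, 9 in all; no cell discontinues on a single reading. The count only shows that this is a continue-or-hold grid, as one would expect for patients without symptoms. It is not a likelihood and does not measure the error.

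**What follows from reading item 2 literally?** First, symptomatic patients with reduced LVEF are sent to that grid, whereas item 1 and the symptomatic list discontinue. Second, Section 6.1.7 has no line left for asymptomatic decline.

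**Which of the two words is wrong?** Three features favour *asymptomatic* in item 2.

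- Item 1 already deals with symptomatic heart failure.
- Items 3 and 4 split bradycardia in the same way, stopping drug for symptoms and taking a milder course without them.
- Appendix F itself separates a grid for asymptomatic falls from a discontinue list for symptomatic events.

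This is an inference. If *symptomatic* was intended, the appendix heading would be the error, and one of the two would still need correction.

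**The case against.** The strongest reply is that the slip corrects itself in use. A site following item 2 must open Appendix F, where the heading above the table states its scope and symptomatic events have their own section. Item 1 stops pazopanib for symptomatic heart failure without asking for a confirmed diagnosis. Section 6 and Section 6.1.1 deal with non-hematologic toxicity of Grade 3 or higher. All of this stands, and it is why the point is small. It does not reconcile the two texts, and nothing else in the document does.

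A reader might also infer more than the documents support.

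- *That the table would keep a symptomatic patient on pazopanib until two consecutive or three intermittent holds.* The Appendix F bullet on three intermittent holds lets the investigator stop permanently before the third. Section 5.4 also ends treatment, at any grade, when the investigator judges the patient's condition unacceptable for continuing.
- *That an identifiable group of symptomatic patients below Grade 3 is exposed.* Grading follows CTCAE version 4.0 (Section 7.2), whose definitions for LVEF decline and heart failure are not reproduced here. The documents do not show whether such a group exists or how large it would be.
- *That the plan wrongly omits a hold while CHF is being confirmed, given Section 6.1.9, where* "Pazopanib should be held in patients with symptoms/signs suggestive of RPLS, pending work-up and management". An explicit hold for one toxicity does not make its absence for another an error. Item 1 already lets a clinician act on judgment, and a hold pending work-up is a separate clinical choice. A rule for all patients with cardiac symptoms would also catch symptomatic bradycardia, for which item 3 stops ARQ 197 and not pazopanib. It could cost evaluability too. Section 5.1.1 requires a dose-escalation patient without DLT to have at least 80% of planned 28-day doses, and a six-day hold in cycle 1 leaves (28 − 6)/28 = 22/28 = 78.6% of the pazopanib doses.

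**Conclusion.** The inconsistency holds: item 2 names a population that the table it cites does not cover. Confidence in the mismatch is high, because it rests on two lines of current text. The direction of the correction is an inference from the surrounding rules, though a strong one.

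The size is minor. The documents give no rate for symptomatic LVEF falls without heart failure, so no patient count can be given, and the existing safeguards limit any harm. Nothing here touches the MTD determination, the MET and phospho-MET analyses or the sample size.

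**What to change.** In Section 6.1.7 item 2, change *symptomatic* to *asymptomatic*. Optionally add a short pointer: for symptomatic cardiac events, see item 1 and the Symptomatic Cardiac Events list in Appendix F. Leave Appendix F as it is, and do not attach a new hold rule to this correction.

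The cost is one word, or one word and a clause, in an amendment. No patient would have an added scan or visit, and the correction itself introduces no new hold.
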